Assessing the Performance of Artificial Intelligence (AI)-augmented Electronic Health Record (EHR) Data Abstraction for Clinical Trial Patient Screening

Study Protocol

NCT06561217

Version date: January 2025

Outline

1. Abstract
2. Overall objectives
3. Aims
 - 3.1 Primary outcome
 - 3.2 Secondary outcomes
4. Background
5. Study design
 - 5.1 Design
 - 5.2 Study duration
 - 5.3 Target population
 - 5.4 Accrual
 - 5.5 Key inclusion criteria
 - 5.6 Key exclusion criteria
6. Subject recruitment
7. Subject compensation
8. Study procedures
 - 8.1 Consent
 - 8.2 Procedures
9. Analysis plan
10. Investigators
11. Human research protection
 - 11.1 Data confidentiality
 - 11.2 Subject confidentiality
 - 11.3 Subject privacy
 - 11.4 Data disclosure
 - 11.5 Data safety and monitoring
 - 11.6 Risk/benefit
 - 11.6.1 Potential study risks
 - 11.6.2 Potential study benefits
 - 11.6.3 Risk/benefit assessment

1. Abstract

The identification of eligible patients for clinical trials is a key component - and a rate-limiting step - of the clinical research enterprise. Currently, the process of identifying eligible patients relies on manual chart review by clinical research staff, which can be time-consuming, labor intensive and prone to human error. As a result, many eligible patients may be overlooked and opportunities for trial participation may be missed: this is particularly true in the oncology space, where fewer than 5% of adult cancer patients enroll in trials. The integration of AI technology into the clinical trial patient screening process has potential to improve trial participation rates and the generalizability of research findings. This study aims to assess the performance (accuracy, efficiency) of AI-augmented patient identification and inform optimal integration of AI technology into clinical research screening processes.

2. Overall objectives

The objective of this study is to assess and compare the accuracy and efficiency of three different approaches to abstracting clinical data used to identify oncology patients who meet the inclusion criteria for participation in clinical trials. The three approaches under evaluation include: (1) an autonomous AI algorithm (Mendel AI; developed by artificial intelligence startup company Mendel) which analyzes patient medical records to extract relevant clinical facts (“AI-alone”); (2) a human researcher who manually reviews patient charts as per the current norm/practice (“Human-alone”); and (3) a human researcher utilizing AI augmentation (“Human+AI”), where Mendel AI serves as a supportive tool in the decision-making process by providing the researcher a list of elements abstracted by the AI algorithm and a rank-order list of patients most likely to meet inclusion criteria for a trial.

The study primarily aims to compare (1) the chart-level accuracy of the Human+AI collaboration relative to Human-alone given the relevance of this comparison for real-world clinical workflows, defined by the percentage of pre-identified chart elements classified correctly compared against a predetermined “gold standard”; and (2) the efficiency of the Human+AI vs. Human-alone arms, defined by the time per chart review in minutes, measured for each chart.

Our hypotheses are (1) the Human+AI arm will be non-inferior in accuracy when compared to the Human-alone arm, in relation to a predetermined “gold standard”, and (2) that a Human+AI arm will be superior in speed of abstraction when compared to Human-alone screening.

The identification of eligible patients for clinical trials is a critical component of clinical research, as it directly impacts patient recruitment, study enrollment, and the generalizability of research findings. Currently, the process of identifying eligible patients often relies on manual chart review by clinical research staff, which can be time-consuming, labor-intensive, and prone

to human error. Consequently, eligible patients may be overlooked, and opportunities for trial participation may be missed. The integration of AI technology into the patient identification process has the potential to enhance the accuracy and efficiency of this critical task, leading to improved clinical trial recruitment and outcomes.

This study holds important implications for the field of clinical research by evaluating the effectiveness of AI-augmented patient identification compared to traditional manual methods and autonomous AI algorithms. By examining the strengths and limitations of each approach, the study will provide valuable insights into the optimal integration of AI technology in clinical research processes. Furthermore, the results of this study have the potential to benefit patients by improving their access to clinical trials and increasing awareness of available treatment options. For clinical research institutions, enhancing the efficiency of patient identification can lead to more effective use of research resources and the potential for accelerated clinical trial timelines. Ultimately, the findings of this study may contribute to advancements in clinical research practices, promoting more equitable access to trials and facilitating the development of innovative treatments for patients with cancer.

3. Aims

3.1 Primary

Aim 1: Compare the **accuracy** of the Human+AI vs. Human-alone arms, in relation to a “Gold Standard” determined by multiple human abstractors with no time limitation.

3.2 Secondary

Aim 2: Compare the **efficiency** of the Human+AI vs. Human-alone arms

4. Background

Insufficient patient enrollment in clinical trials is a significant challenge faced by the clinical trials community, and it is often considered the rate-limiting step in completing clinical trials. The traditional approach to determining patient eligibility for clinical trials is manual eligibility screening (ES), which requires a labor-intensive review of patient records, leading to a high workload for clinical staff and a potential delay in trial enrollment. The problem of insufficient patient enrollment is symbolized by the fact that less than 5% of patients with cancer participate in clinical trials. [1] The manual eligibility screening process is resource-intensive, and reducing the burden of screening is a priority for improving trial participation rates and the efficiency of clinical research.

Recent advancements in artificial intelligence (AI) and natural language processing (NLP) offer potential solutions to this challenge. These technologies have the capability to automatically detect patients' eligibility for clinical trials by mapping coded clinical trial eligibility criteria to corresponding clinical information extracted from electronic health records (EHRs). This process involves extracting relevant eligibility criteria from clinical notes using machine learning-based NLP applications and comparing these extracted criteria with reference criteria from trial descriptions. Studies have shown that machine learning-based NLP applications provide high accuracy in extracting eligibility criteria from clinical notes and determining trial eligibility, with recall rates of up to 90.9% and precision rates of up to 89.7%. [2]

Automated ES algorithms have demonstrated success in significantly reducing the workload of clinical staff involved in trial-patient matching, thereby increasing the trial screening efficiency of oncologists. Additionally, the use of AI-based tools has the potential to enable participation of smaller practices, which are often left out from trial enrollment due to resource constraints. The integration of AI and NLP technologies in the clinical trial eligibility screening process can play a crucial role in increasing total patient enrollment, the speed of enrollment, as well as expanding access to trials, and enhancing the execution of clinical research.

5.1 Design

In this experimental study, we will employ a three-arm design including (1) AI-alone, (2) Human-alone, (3) Human+AI to assess the accuracy of abstracting clinical elements from the patient chart. The accuracy of the abstraction will be compared against a pre-made “gold standard”. As detailed elsewhere, the study is powered for a direct comparison of the human alone vs human + AI arms as a non-inferiority analysis. For Arm 1, an autonomous AI algorithm (Mendel AI) will analyze patient medical records to extract relevant clinical elements (“AI-alone”). For Arm 2, a human researcher will manually review patient charts as per the current norm/practice (“Human-alone”). For Arm 3, a human researcher will utilize Mendel AI augmentation such that Mendel AI serves as a supportive tool in the decision-making process by providing the researcher a list of elements abstracted by the AI algorithm and a rank-order list of patients most likely to meet inclusion criteria for a trial (“Human+AI”). **For this study, we will**

only be using information from deidentified patient charts in Mendel's database. No Penn data will be utilized in this study.

We will employ 2 clinical research coordinators (CRCs) who will review and abstract specific clinical elements while reviewing the patient's electronic health record (EHR) which will include both "structured" (machine-readable) and "unstructured" (traditionally non-machine-readable; Mendel AI is uniquely capable of processing) data. To ensure no inter-rater differences in accuracy the CRCs will be assessed on a practice set of three charts and must meet an 80% threshold of agreement on review elements as well as concordance in chart-level accuracy as measured by Cohen's Kappa (threshold 0.6).

The components of the EHR that may be reviewed to abstract the data elements of interest may include:

- Physician Progress Notes
- Radiology Reports
- Pathology Reports
- Laboratory Reports
- Genetic/molecular sequencing and other genetic testing results
- Discharge Summaries
- Infusion Therapy reports

To help assess accuracy, the "Gold Standard" (to which all study arms will be compared) will be a manually annotated version based on review of at least 2 human abstractors (plus a tie-breaker if there is a discrepancy). This process will be led by the Mendel team, with independent oversight by the Penn research team to ensure consistency.

First, the Mendel AI algorithm will review all patient charts, producing a machine-annotated version of each chart with AI-abstracted elements (AI-alone). Next, each CRC will review all patient charts. Each CRC will review half of their charts manually (Human-alone) and half of their charts using the machine-annotation and rank-order list (Human+AI). The order of review will be randomized such that manual reviews and AI-assisted reviews will be mixed, and such that each CRC will review half of the charts manually and half of the charts with AI assistance.

Secondary aim metrics (Efficiency) will be assessed by tracking the volume of completed prescreens per unit of time.

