8.2 Procedures

Our study will follow the design outlined above (section 5.1).

There is no informed consent needed for the use of this data. There will be no participant recruitment or compensation. Potential risks and benefits of the study are reported elsewhere (section 11.6).

Two CRCs will be hired to analyze de-identified patient data. CRCs will access the data via a password-protected portal, using a UPHS desktop and/or laptop. De-identified patient chart data will be included for analysis based on having a tumor type of interest. They will then review patient charts and record clinical elements of interest in the Mendel abstraction tool, which will be secured in a HIPAA-compliant external enclave. Summary-level data will be exported into datasheets for analysis. These datasheets will only be used and analyzed on UPHS equipment, or shared via HIPAA-compliant means.

Data will be analyzed using statistical software including Excel, R code, and STATA. For details of the analysis plan, see section 9.

Data elements that will be abstracted across all arms of the study include the following (the below list may change slightly pending further discussion among the research team):

Cancer Type and Staging

- Cancer Type
- Stage - Tumor
- Stage - Node
- Stage - Mets

Performance

- ECOG Performance Status

Prior Systemic Treatment

- Any Prior Platinum Therapy (e.g., Cisplatin, Carboplatin, Oxaliplatin)
- Any Other Prior Chemotherapy (e.g., 5-fluorouracil, Leucovorin, Capecitabine, Irinotecan, Pemetrexed, Paclitaxel, Docetaxel, Gemcitabine)
- Any Prior Immunotherapy (e.g., Atezolizumab, Nivolumab, Pembrolizumab)

Biomarkers for CRC

- KRAS
- MSI-H
- MSS
- BRAF
- HER2
- NTRK
- DPYD

Biomarkers for NSCLC

- EGFR
- ALK
- ROS1
- KRAS
- BRAF
- NTRK
- cMET
- RET
- PDL1

Others

- Outcomes (remission, residual disease, recurrence, loco-regional recurrence, distant recurrence)
- Responses (complete response, stable disease, partial response, mixed response, disease progression)

9. Analysis plan

The primary study will be powered on a retrospective paired, non-inferiority design to evaluate abstraction accuracy of elements commonly used to help screen patients for clinical trials. The two arms are (1) human reviewers versus (2) human reviewers utilizing predictions from Mendel AI. The primary outcome, the percentage of gold standard items correctly abstracted, will be measured for each chart. Noninferiority can be established by comparing the difference in the

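### The kappa criterion for qualifying the two coordinators does not work as written on three charts, and neither qualification criterion can exclude a coordinator difference; the effect on the primary comparison is added variance, not material bias

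*Combined protocol and SAP*

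**What the plan says.** Section 5.1 (Design) states: "We will employ 2 clinical research coordinators (CRCs". It gives their qualification test a purpose: "To ensure no inter-rater differences in accuracy the CRCs will be assessed on a practice set of three charts". The coordinators "must meet an 80% threshold of agreement on review elements as well as concordance in chart-level accuracy", the latter measured by Cohen's kappa with a threshold of 0.6.

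Chart-level accuracy is defined in section 2 ("defined by the percentage of pre-identified chart elements classified correctly") and again in section 9 ("The primary outcome, the percentage of gold standard items correctly abstracted, will be measured for each chart"). It is therefore one percentage per chart and reader.

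For the main review, section 5.1 says that "each CRC will review all patient charts". Each coordinator does half of the charts manually and half with AI assistance, in randomized, mixed order. Section 9 specifies a paired test on within-chart differences, with a margin of 0.05 and no coordinator term.

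The plan does not give categories or weights for the kappa, or a rule for an undefined value. It does not say whether the 80% is agreement between the coordinators or with the gold standard.

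**The concern.** Cohen's kappa compares two raters' assignments of units to categories. Here the quantity is a percentage and there are three units. A statistic on three units has very few possible values, so a 0.6 threshold may not mean what it appears to mean. When both coordinators do uniformly well, it may have no value at all, and the study team would then have to invent a pass rule after seeing the practice results.

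The stated purpose is also strong. A chart's paired difference sets one coordinator's AI-assisted read against the other's manual read, so coordinator differences enter every within-chart difference. If the practice test cannot rule them out, the analysis should deal with them.

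**Working it through.** The thresholds are chosen cut-offs, so there is no derived figure to reproduce. The check is whether they can do what is asked of them.

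**Inputs.** Section 5.1: 3 practice charts, 2 coordinators, kappa 0.6, agreement 80%. Section 9: margin 0.05, 400 charts, one-sided 5%, power above 90%. Section 8.2: the list gives 10 common elements plus 7 biomarkers for colorectal cancer or 9 for NSCLC, so 17 or 19 per chart. Section 9 instead refers to 12 criteria. Three charts therefore give 3 × 12 = 36, 3 × 17 = 51 or 3 × 19 = 57 items. Which count applies is an assumption, because the list may still change.

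**1. Kappa on three charts.** kappa = (po − pe)/(1 − pe), where po is observed and pe is chance agreement.

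- Two categories, all 64 pairs of ratings enumerated: kappa is 1, 0.4, 0, −0.5, −0.8 or undefined.
- More categories, exactly one disagreement: po = 2/3. The smallest possible pe is 2/9 (the two agreed charts in different categories, nothing else shared). Then kappa = (6/9 − 2/9)/(7/9) = 4/7 = 0.571.
- The highest kappa with any disagreement is 0.4 with two categories, 0.50 with three and 0.571 with four or more.
- All ratings in one category: po = pe = 1, so kappa = 0/0.

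So 0.6 requires identical ratings on all three charts and some variation between charts.

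**2. How often kappa is undefined.** Suppose charts are classed as accurate or not, each is accurate with probability p (assumed), and the coordinators agree perfectly. Then P(undefined) = p³ + (1 − p)³.

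| p | P(undefined) |
|---|---|
| 0.80 | 0.512 + 0.008 = 0.52 |
| 0.90 | 0.729 + 0.001 = 0.73 |
| 0.95 | 0.857 + 0.000 = 0.86 |

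If the exact percentages serve as categories, two equally skilled, independent coordinators with 90% accuracy per element (assumed) match on all three charts with probability 0.023 (12 elements), 0.013 (17) or 0.011 (19).

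**3. The 80% criterion.** It is computable but imprecise. Clopper-Pearson 95% intervals, ignoring clustering within charts, are 0.64–0.92 (29/36), 0.67–0.90 (41/51) and 0.68–0.90 (46/57). If the coordinators differ in correctness on 20% of items, the 95% half-width for their accuracy difference is 1.96 × √(0.2/N): 0.146, 0.123 and 0.116 for N = 36, 51 and 57. A result near the threshold cannot show that the coordinators are equally accurate.

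**4. Effect on the primary comparison.** Call the coordinators A and B. With equal, complementary halves, the mean paired difference is

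½(AI_A − Human_B) + ½(AI_B − Human_A) = ½[(AI_A − Human_A) + (AI_B − Human_B)].

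This is the average of the two within-coordinator effects, so a constant gap g drops out. It moves the differences by +g in one half and −g in the other, which adds g² to their variance.

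Section 9 states no SD. Its sample size formula with n = 400, D = 0, margin 0.05, one-sided 5% and 90% power implies σ of about 0.34. With n = 400, power = Φ(0.05 × √400/σ − 1.645) = Φ(1/σ − 1.645).

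| σ (assumed) | g = 0 | g = 0.10 |
|---|---|---|
| 0.34 | 90% | √(0.1156 + 0.01) = 0.354, power about 88% |
| 0.15 | above 99% | √(0.0225 + 0.01) = 0.180, power above 99% |

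**The case against.** The strongest reply is that the design already protects the comparison. Each coordinator contributes half of the charts to each arm, in mixed order, so the practice test is not what keeps the arms comparable. This stands. A reader might infer that a coordinator gap would bias the non-inferiority result; step 4 shows that it would not if the halves are complementary. Section 5.1 does not say in so many words that they are, but one read per arm per chart presupposes it.

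A reader might also set the 20% disagreement that the rule tolerates against the 5-point margin. These are unlike quantities. Two equally accurate coordinators can disagree on 20% of items with no difference in mean accuracy, and even a real gap largely cancels between the arms.

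Another reply is that a weighted or element-level kappa was meant. The text says neither. Either would avoid the all-or-nothing behavior, but not support the stated purpose. Accuracies of 60/80/95 against 50/70/85, a constant 10-point gap, give a quadratic-weighted kappa of 0.80 and pass. An element-level kappa is defined but imprecise: at a true value of 0.6 with 57 items and 80% accuracy (assumed), its 95% sampling range is 0.30 to 0.84.

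Finally, an undefined kappa does not always signal a good result. It also arises if both coordinators are inaccurate on all three charts. That is a further reason why the rule needs a stated outcome for this case.

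**Conclusion.** The point holds as a minor defect with a cheap remedy. On the literal reading, the kappa criterion amounts to requiring identical, non-constant ratings on three charts, and it has no outcome when all ratings fall in one category. The 80% criterion can be computed, but neither criterion supports the claim that coordinator differences in accuracy are excluded.

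The documents do not support a claim that the primary comparison is materially biased. Given complementary halves and a roughly constant gap, the cost is variance: about 2 percentage points of power for a 10-point gap at σ = 0.34, and next to nothing at σ = 0.15. Both σ values and the gap are assumptions, since the plan states none of them.

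**What to change.** 1. In section 5.1, delete the chart-level kappa criterion. Alternatively, compute agreement on element-level correct/incorrect scores against the gold standard, pooled over the practice charts (36 to 57 items). Scoring correct/incorrect avoids mixing elements with different answer sets. State whom the 80% compares, and give a rule for an undefined kappa. If a kappa is kept, note that it stays imprecise and can conflict with the 80% rule when accuracy is high. With both coordinators at 90% accuracy, pe = 0.81 + 0.01 = 0.82. Then 80% agreement gives kappa = (0.80 − 0.82)/0.18 = −0.11, and kappa 0.6 needs 0.82 + 0.6 × 0.18 = 92.8% agreement.

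2. Replace the purpose clause with a statement that the coordinator difference will be estimated in the main data. Section 9 has a paired test and no regression model, so the extension must be written out: regress the within-chart difference (Human+AI minus Human-alone) on an indicator coded +1 or −1 for which coordinator did the AI-assisted read. Test the intercept against −0.05. With equal halves the intercept equals the plain mean difference. The slope estimates the coordinator gap averaged over the arms, and its contribution leaves the residual variance. State in section 5.1 that the two coordinators' halves are complementary.

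The cost is some wording, slightly more analysis work and one degree of freedom. No new charts or staff are needed.

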mean proportion correct between the human-augmented and Human-alone arms with a predefined non-inferiority margin, Δ .

The one-sided hypotheses to test noninferiority of average chart-level accuracy of a Human+AI abstraction approach, compared with a Human-alone approach are outlined below:

$$H_0: \mu_{h-ai} - \mu_h \leq -\Delta \text{ (Null hypothesis)}$$

$$H_a: \mu_{h-ai} - \mu_h > -\Delta \text{ (Alternative hypothesis)}$$

Test statistic:

$$T_n = \frac{(\mu_{h-ai} - \mu_h) + \Delta}{\sqrt{\frac{Var(D)}{n}}}$$

Sample size equation for a noninferiority, paired study design:

$$n = \frac{(z_{1-\beta} + z_{1-\alpha})^2 \sigma^2}{((\mu_{h-ai} - \mu_h) + \Delta)^2} = \frac{(z_{1-\beta} + z_{1-\alpha})^2 \sigma^2}{(D + \Delta)^2}$$

As a secondary analysis, we will test the superiority of the Human+AI arm for achieving greater average chart-level accuracy, compared with the Human-alone arm. Our hypotheses are:

$$H_0: \mu_{h-ai} \leq \mu_h \text{ (Null hypothesis)}$$

$$H_a: \mu_{h-ai} > \mu_h \text{ (Alternative hypothesis)}$$

Sample size equation for a superiority, paired study design:

$$n = \frac{(z_{1-\beta} + z_{1-\alpha})^2 Var(D)}{(\mu_{h-ai} - \mu_h)^2}$$

Parameter	Description
μ_{h-ai}	Mean proportion of criteria correctly abstracted by AI-augmented human reviewers
μ_h	Mean proportion of criteria correctly abstracted by Human-alone reviewers
$D = \mu_{h-ai} - \mu_h$	Mean difference in chart-level accuracy between arms
Δ	Non-inferiority margin, set as 0.05 for conservative sample size estimates.
$z_{1-\beta}$	Critical value at $1-\beta$, where $1-\beta$ represents the desired power and β represents Type II error

$Z_{1-\alpha}$	Critical value at $1-\alpha$, where α = Type I error
σ^2	$n^* \text{Var}(D)$, where n is the sample size and $\text{Var}(D)$ is the variance of the mean difference in chart-level accuracy

*Note: μ_{h-ai} , μ_h , $\Delta > 0$.

From our initial calculations, 400 individual patients will achieve an estimated statistical power greater than 90% for this non-inferiority study with a Type I error of 5%. This was determined from simulations for different realistic parameter scenarios for TNR, event rate, and concordance assumptions showing that the needed sample size rarely exceeded 400.

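### Does vendor leadership of the gold standard bias the accuracy comparison enough to require a change to the plan?

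*Combined protocol and SAP*

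**What the plan says.** Section 2 names Mendel as developer of the algorithm and defines chart-level accuracy as "defined by the percentage of pre-identified chart elements classified correctly compared against a predetermined" gold standard. Section 3.1 says that standard is "determined by multiple human abstractors with no time limitation". Section 5.1 calls it pre-made, makes it the comparator for all three arms, and describes it as "a manually annotated version based on review of at least 2 human abstractors (plus a tie-breaker if there is a discrepancy". On who runs it, the same section says: "This process will be led by the Mendel team, with independent oversight by the Penn research team to ensure consistency".

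Each coordinator reviews half of the charts manually and "half of their charts using the machine-annotation and rank-order list (Human+AI"), in mixed random order (section 5.1). Section 8.2 has coordinators enter their findings in the vendor's abstraction tool and draws no distinction by arm. Section 9 tests non-inferiority of the mean chart-level difference with a margin of 0.05 ("Non-inferiority margin, set as 0.05 for conservative sample size estimates"). It adds a sensitivity analysis with a looser matching rule against the same gold standard.

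**The concern.** The party with an interest in the result leads the process that decides which answers count as correct. Two checks are written. The tie-breaker is triggered by disagreement between abstractors. The academic team's oversight has consistency as its stated aim and no described procedure. Neither is said to re-read a label on which both abstractors agree, so a convention shared inside the vendor's process could pass through both.

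Such a convention need not be neutral between arms. If the AI follows it too, only the Human+AI coordinators are prompted toward it. The element list leaves some room: "Outcomes (remission, residual disease, recurrence, loco-regional recurrence, distant recurrence") puts a general category beside two specific ones that overlap with it. No accuracy analysis in section 9 uses a second reference. In the worst reading, a non-inferiority claim could not be separated from mere closeness to the vendor's labels.

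**Working it through.** **The plan's own figure.** Section 9 says "400 individual patients will achieve an estimated statistical power greater than 90" per cent. Its paired formula is n = (z₁₋β + z₁₋α)²σ² / (D + Δ)². With one-sided α = 0.05, power 90% and Δ = 0.05, the z-sum is 2.926. Neither σ nor D is given, so 400 cannot be reproduced. Solved backwards at n = 400, the largest σ that gives 90% power is 0.05 × 20 / 2.926 = 0.342 for D = 0, and 0.273 or 0.205 for D = −0.01 or −0.02. The sample size is not in dispute here; these values only scale what follows.

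**Size of a shift.** Let f be the share of elements on which the reference and the AI share a label that an independent reference would reject. On such an element the assisted coordinator adopts the AI label with probability a, and otherwise behaves as Human-alone, who is independently correct with probability h and gives the shared label with probability s.

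- Measured minus true difference per affected element: a(1 − s) + ah = a(1 − s + h).
- Average shift: b = f × a(1 − s + h), at most 2f (a = 1, h = 1, s = 0).

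Minimum f for a shift of the whole margin: 0.05 / 2 = 2.5%. For 1 point: 0.01 / 2 = 0.5%. The documents give no value for a, h, s or f, so the inputs below are assumed.

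| h, s | a | a(1 − s + h) | f for 5 points | f for 1 point |
|---|---|---|---|---|
| 0.9, 0 | 0.7 | 1.33 | 3.76% | 0.75% |
| 0.9, 0 | 0.5 | 0.95 | 5.26% | 1.05% |
| 0.9, 0 | 0.3 | 0.57 | 8.77% | 1.75% |
| 0.5, 0.3 | 0.7 | 0.84 | 5.95% | 1.19% |
| 0.5, 0.3 | 0.5 | 0.60 | 8.33% | 1.67% |
| 0.5, 0.3 | 0.3 | 0.36 | 13.89% | 2.78% |

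**Elements per chart.** Section 9 speaks of 12 criteria, so 2.5% is 0.3 per chart. Section 8.2 lists 4 + 1 + 3 + 7 + 2 = 17 elements for colorectal charts and 4 + 1 + 3 + 9 + 2 = 19 for NSCLC, where 2.5% is 0.43 or 0.48 per chart. Percentages are therefore safer than counts.

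**Direction.** A simulation (400 charts, 17 elements, AI and humans each 85% correct, 40% adoption, 30% of human errors falling on the AI's wrong value, true difference about 0) gave observed differences of +0.014, +0.036 and +0.072 when wrong reference labels matched the AI on 2%, 5% and 10% of elements. The formula agrees: 0.4 × (1 − 0.045 + 0.85) = 0.722, times f gives 0.014, 0.036 and 0.072. When the wrong labels were unrelated to the AI, the observed difference stayed at about 0. Unrelated errors at rate e only shrink a true difference by a factor between 1 − 2e and 1 − e: at e = 5%, −0.05 reads between −0.045 and −0.0475. The direction thus depends on the match with the AI, not on vendor leadership alone.

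**Consequence, if a shift exists.** At a true difference of −0.05, the chance of claiming non-inferiority is Φ(b / (SD/√400) − 1.645). At SD 0.342 it rises from 5% to 14.5% for b = 0.01 and 31.8% for b = 0.02. At an assumed SD of 0.20 it rises to 26% and 64%.

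**What an independent re-reading of 60 charts would show.** At f = 1%, the expected shift and the simulated 95% half-width, in points, are:

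| a, h, s | Shift | Half-width |
|---|---|---|
| 0.7, 0.9, 0 | 1.33 | 1.20 |
| 0.5, 0.9, 0 | 0.95 | 1.01 |
| 0.5, 0.5, 0.3 | 0.60 | 1.00 |
| 0.3, 0.5, 0.3 | 0.36 | 0.94 |

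In three of four cases the half-width exceeds the shift. With 60 × 12 = 720 elements and no shared label found, the upper 95% bound on f is 1 − 0.05^(1/720) = 0.415%, which excludes shifts above 0.83 points. That needs a second reference that makes no errors of its own. If it wrongly rejected an assumed 2% of labels on which gold standard and AI are both right, about 14 of 720 would look like shared labels. The upper bound on f would then be about 3.0%, or 6.0 points of shift, which is more than the margin.

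**The case for a change.** The strongest case for acting is that the facts are not in doubt. The developer leads the sole reference, no check on agreed labels is written down, and the looser-match analysis keeps the same reference. A shift of only 1 point would raise the error rate noticeably, as shown above. Stored charts could be re-read after coordinator review without touching the primary analysis. At an assumed 30 to 60 minutes per chart, two readers of 60 charts would need 60 to 120 hours. All of that stands.

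What does not stand is the step from possible to probable.

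- That the written checks reach only disagreements is one reading. Oversight for consistency may equally mean consistent application of definitions, which could reach agreed labels.
- A gold standard that is manual, pre-made and predetermined is most naturally read as made by people, without AI output, before the arms are scored. In section 5.1, manual review is the opposite of review with machine annotation.
- The recurrence example is a difference in granularity. The looser matching rule might accept such pairs (the rule is not given), in which case a changed result would be a signal.
- Categories built into the vendor's tool would be common to both arms.
- Each coordinator works in both arms in mixed order, so a convention learned from assisted charts can carry into manual ones. That raises s, lowers h, and shrinks a(1 − s + h).

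**Conclusion.** The point is a fair caution for reading the results, but it does not call for a change. A shift toward Human+AI rests on an assumption: agreed reference labels that are both wrong and equal to the AI output. If f = 0, or if coordinators never adopt such a label, there is no shift. A shift the size of the margin needs at least 2.5% of elements affected in the extreme case, and 3.8% to 13.9% under the illustrative inputs.

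Two remedies come to mind, and neither earns its place. A sentence saying that the abstractors and tie-breaker work from raw charts without AI output would write down what the plan's description already implies; that is a gap the study team would fill sensibly. A second, academic-led abstraction costs extra readers, could exclude only a large shift, and depends on a second reference that may itself err. Manual annotation by at least two people without a time limit, with a tie-breaker and academic oversight, is a fair trade-off. Vendor leadership is stated in the protocol, so readers can weigh it as a limitation.
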